*** Confidentiality Statement**

The information contained in this document is privileged and confidential. Any disclosure is prohibited unless such disclosure is required by applicable laws and regulations. Persons to whom the information is disclosed must be informed that the information is privileged and confidential and it may not be further disclosed by them.

PROTOCOL SYNOPSIS

Title

A Randomized, Placebo-Controlled, Double-Blind, Multicenter Study to Evaluate Efficacy and Safety of Oral BT-11 in Moderate to Severe Crohn's Disease

Objectives and Endpoints

Primary Objective

The primary objective of this study is to assess the proof-of-concept efficacy and safety of oral BT-11 in inducing clinical remission and endoscopic response at Week 12 in subjects with moderately to severely active Crohn's disease (CD).

Study Design

This is a phase 2, randomized, placebo-controlled, double-blind, parallel-group, multicenter study. The purpose of this study is to evaluate the proof-of-concept efficacy and safety of oral BT-11 compared to placebo in subjects with moderately to severely active CD to estimate the effect size and efficiently power future phase 3 studies. Approximately 100 sites will participate from Europe and the United States.

A total of 150 subjects were planned to be randomized in a 1:1 ratio, in a centralized manner, to receive BT-11 880 mg or placebo. Each of the treatment arms will comprise 75 subjects. The randomization will be stratified by prior exposure to biologic therapy for CD (yes/no; exposed population limited to 50% of total sample) and corticosteroid use at baseline (yes/no).

The study will consist of a 28-day screening period, a 12-week induction period, an 18-week maintenance period, and a 2-week post-treatment safety follow-up period.

A final analysis of induction phase data (induction data lock and analysis), of the Week 12 primary endpoint, Week 12 key ranked secondary endpoints, and Week 12 adverse event (AE) listings, will be conducted after all subjects have reached Week 12. At Week 12, subjects who are clinical responders (defined by a Crohn's Disease Activity Index [CDAI] decrease from baseline ≥ 100 points or CDAI < 150) or endoscopic responders (defined by a 50% reduction from baseline in the Simple Endoscopic Score for Crohn's Disease [SES-CD] score), and meet all other maintenance continuation requirements, may continue blinded study drug until central endoscopy results are available (within approximately 1 week of the endoscopy) for confirmation of eligibility for the additional 18-week maintenance period. If a subject is a potential endoscopic responder at Week 12 and requires centrally read confirmation of SES-CD score as a qualifying continuation criteria (i.e., doesn't qualify for maintenance based on clinical response or remission alone), then the SES-CD score must be confirmed by central reading. Subjects who are non-responders at Week 12, or who lose response during the maintenance period, or who complete the Week 30 study will be eligible for a separate open-label extension (OLE) study.

Study Population

The study will include 150 subjects with moderately to severely active CD. Subjects with prior exposure to biologic therapy will be limited to 50% of the total sample. After 75 subjects with prior exposure to biologic therapy have been randomized into the induction period, recruitment will be limited to biologic naïve subjects.

Key inclusion criteria: subjects aged 18 to 75 years with a diagnosis of CD for at least 3 months; moderately to severely active CD as defined by: a CDAI score of 220-450, and an SES-CD scored ≥ 6 (≥ 4 for isolated

ileitis) (centrally read); prior biologic must have stopped at least 8 weeks before randomization (or within 4 weeks prior to randomization, if no detectable drug levels by validated or commercial assay) and previous biologic treatment failure is limited to 1 class of biologic (if applicable); 5-aminosalicylates (max 4.8 g/day) and oral corticosteroids (max 20 mg/day prednisone or equivalent) must be stable for the duration of the 12-week induction period.

Key exclusion criteria: ulcerative colitis; imminent risk of ileocolectomy; symptomatic bowel stricture, ostomy or ileoanal pouch, stenoses, or short gut syndrome; recent (within 2 months) abscess, unless drained and treated at least 6 weeks before randomization; history of bowel resection or diversion within 3 months prior to screening; use of apheresis \leq 2 weeks prior to screening; treatment with an immunosuppressant within 25 days prior to randomization; known current bacterial or parasitic pathogenic enteric infection; live virus vaccination within 12 weeks of screening.

Maintenance continuation criteria: meeting eligibility requirements for clinical response and/or clinical remission at Week 12 or endoscopic response at Week 12, centrally read confirmation of response is received within 1 week of completing the Week 12 visit, and agreeing to a corticosteroid tapering regimen starting at Week 12 with maintenance of stable doses of any other nonprohibited concomitant medications for CD during the rest of the study.

Treatments, Dosage, and Administration

Subjects will be randomized to receive BT-11 880 mg or placebo once-daily for 12 weeks during the induction period of the study. Subjects who continue on to the maintenance period will remain in the same blinded treatment group to which they were originally randomized.

Authorized personnel at the investigative site will administer the first dose of the study drug or placebo. This study is double-blinded. Alls administered (placebo and BT-11) will be identical in appearance and size. According to the randomization scheme, each subject will receive PE bottles of either the study drug or placebo.

Statistical Analysis Plan

Protocol Number: BT-11-202; Phase 2

**A Randomized, Placebo-Controlled, Double-Blind, Multicenter Study to Evaluate Efficacy
and Safety of Oral BT-11 in Moderate to Severe Crohn's Disease**

**Version 1.0
01 April 2021**

Sponsor: Landos Biopharma Inc.

Clinical Research Organization: [redacted]

Statistical Methods

A total sample size of 150 subjects randomized in a 1:1 ratio to BT-11 880 mg or placebo (75 subjects per treatment group) is expected to provide evaluable data on approximately 74 subjects per group at Week 12 (1% attrition rate).

Efficacy analyses will primarily be based on the modified intent-to-treat [mITT] analysis set. A robustness analysis of the primary and key secondary efficacy endpoints will also be performed on the per-protocol (PP) analysis set. Statistical tests will be 2-sided and performed at the 0.05 level of significance.

The first coprimary efficacy endpoint is the proportion of subjects achieving clinical remission at Week 12 (defined by a CDAI score < 150). Inference will be determined with a Cochran-Mantel-Haenszel test and stratified with respect to previous use of biologic therapy and corticosteroid use at baseline. As this is a proof-of-concept study, success in this trial is not intimately linked to achieving statistical significance on primary and key secondary endpoints.

The issue of multiplicity of secondary measurements will be handled by statistical testing of these outcomes in a hierarchical fashion. The order of secondary endpoints is described above. If the primary outcome shows significance, tests will be conducted on secondary outcomes until a non-significant p-value is found ($P > 0.05$). Once a nonsignificant p-value occurs, all subsequent significance tests will be considered exploratory in nature.

A data lock and final induction phase analysis of the Week 12 primary endpoint, Week 12 key ranked secondary endpoints, and Week 12 AE listings will be performed when all subjects have completed the induction period (or discontinued study treatment). To minimize any bias being introduced into the analyses, all data associated with the primary and key secondary endpoints during the assessment period must have been monitored, the induction period SAP must be finalized and approved, and the definitions of analysis populations must be finalized (including classification of significant protocol deviations and decision regarding exclusion of any subjects from the induction study analysis) before database lock and unblinding.

As this will be the final analysis of the primary endpoints and key ranked secondary endpoints, no adjustment of type I error will be performed. The induction analysis will be performed by a limited number of preidentified team members who do not have direct site contact or data entry/validation responsibilities. Unblinding details will be specified in the statistical analysis plan or a separate unblinding plan document. Information that may unblind the study during the analyses will not be reported to study sites or the blinded study team until the study has been unblinded.

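### Baseline CDAI is not used in the clinical remission effect estimate wanted for phase 3: a minor, cheap precision improvement beside a valid stratified CMH test

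*Combined protocol and SAP*

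**What the plan says.** The Study Design part of the Protocol Synopsis gives, among the reasons for the trial, "to estimate the effect size and efficiently power future phase 3 studies". Statistical Methods adds that success does not hinge on statistical significance, so the size of the effect and its precision are main products of the study.

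Statistical Methods defines the endpoint: "The first coprimary efficacy endpoint is the proportion of subjects achieving clinical remission at Week 12 (defined by a CDAI score < 150". The method follows directly: "Inference will be determined with a Cochran-Mantel-Haenszel test and stratified with respect to previous use of biologic therapy and corticosteroid use at baseline". These are the randomization factors given in Study Design ("The randomization will be stratified by prior exposure to biologic therapy for CD", plus corticosteroid use at baseline). The endpoint is also to be analysed on the per-protocol set, which changes the analysis set; no other method is named.

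Study Population requires "a CDAI score of 220-450" at entry, so baseline CDAI is known for everyone. It is not a randomization stratum, and the available text does not name it as a covariate. That text also names no estimator or interval for the treatment effect.

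On size, the plan says that the trial is "expected to provide evaluable data on approximately 74 subjects per group at Week 12". On timing, it says that "the induction period SAP must be finalized and approved" before database lock and unblinding.

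**The concern.** A CMH test delivers a p-value. A trial meant to inform phase 3 also needs an estimate of the difference in remission proportions, with an interval, by a method fixed before unblinding. If the method is left open, the effect measure and any adjustment could be chosen after the data are seen.

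The available text also leaves a baseline measurement unused. Remission is CDAI cut at 150, so baseline CDAI is a natural candidate predictor. If it does predict remission, a standardised estimate that adjusts for it has smaller variance than one adjusted for the two strata alone, with no new data. At stake is some precision in the phase 3 planning estimate. The validity of the test is not in question, and its power does not change.

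**Working it through.** **Inputs from the documents.** 150 randomized 1:1, 1% attrition, two-sided 0.05, two binary strata (biologic-exposed capped at 50%), entry CDAI 220-450, remission at CDAI < 150.

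**The plan's own figure.** 75 x (1 - 0.01) = 74.25, or about 74 per group. It reproduces. The available text gives no remission rates or power, so power cannot be checked.

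**Assumptions (none is in the documents).** Remission rates as tabulated; baseline CDAI normal(310, 60) truncated to 220-450; Week 12 CDAI SD 100; correlation r between baseline and Week 12 CDAI among enrolled subjects of 0, 0.3 or 0.5; 50% biologic-exposed and 35% on corticosteroids; strata not prognostic.

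**Estimators compared.**
- Mantel-Haenszel (MH) difference: sum of w_s(p1_s - p0_s) / sum of w_s, with w_s = n1_s n0_s / N_s, and Sato variance.
- Adjusted difference: fit a logistic model with treatment, both strata and baseline CDAI. Predict each subject's remission probability under BT-11 (q1) and placebo (q0), and average q1 - q0 to give d. With A = 1 for BT-11, Y = 1 for remission and pi the proportion allocated to BT-11, the influence value is (A/pi)(Y - q1) - ((1 - A)/(1 - pi))(Y - q0) + q1 - q0 - d. SE = sqrt(sum of squared influence values / (n(n - 5))), n = 148, t with 143 df.

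**Variance ratio, adjusted / MH** (12,000 simulated trials per setting). Equivalent subjects per arm, 74 / ratio, in brackets.

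| Placebo v BT-11 | r = 0 | r = 0.3 | r = 0.5 |
|---|---|---|---|
| 5% v 15% | 1.010 (73.3) | 0.981 (75.4) | 0.942 (78.6) |
| 10% v 25% | 1.007 (73.5) | 0.964 (76.8) | 0.900 (82.2) |
| 20% v 40% | 1.007 (73.5) | 0.961 (77.0) | 0.861 (85.9) |
| 30% v 50% | 1.008 (73.4) | 0.949 (78.0) | 0.854 (86.7) |

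Adjustment is thus worth just under 1 subject per arm fewer at r = 0, 1 to 4 more at r = 0.3, and 5 to 13 more at r = 0.5. Repeat simulations at 20% v 40%, r = 0.5 gave ratios from 0.84 to 0.89.

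**95% CI half-width, in percentage points.**

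| Placebo v BT-11 | MH | Adjusted, r = 0 | r = 0.3 | r = 0.5 |
|---|---|---|---|---|
| 5% v 15% | 9.4 | 9.6 | 9.4 | 9.1 |
| 10% v 25% | 11.9 | 12.1 | 11.8 | 11.4 |
| 20% v 40% | 14.3 | 14.5 | 14.2 | 13.5 |

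**Analytic check at 20% v 40%.** SE = sqrt(0.2 x 0.8/74 + 0.4 x 0.6/74) = 0.0735, and 1.96 x 0.0735 = 14.4 points. If baseline CDAI explains a share R2 of the within-stratum variance of remission, this shrinks by sqrt(1 - R2). R2 = 0.05 (about r = 0.3) gives 14.0; R2 = 0.137 (about r = 0.5) gives 14.4 x sqrt(0.863) = 13.4. The simulated adjusted half-widths are slightly larger because of the small-sample correction.

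**Behaviour.**
- Coverage was 94.4-95.4% (adjusted) and 94.2-95.1% (MH).
- With a true effect, CMH and the adjusted interval disagreed on significance in 2-3%, 5-7% and 10-12% of trials at r = 0, 0.3 and 0.5. CMH and the MH interval disagreed in 1-2%.
- With no effect, rejection at 10% v 10% and r = 0.5 was 4.9% for CMH and 5.5% for the adjusted interval (simulation SE 0.2%). At 20% and 30% the two differed by at most 0.4 points.

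**The case against.** **The text is a summary.** It points to material it does not contain ("The order of secondary endpoints is described above") and leaves unblinding details to the SAP or a separate plan. A summary that names only the primary test is normal. This stands: a reader might infer that the sponsor has no estimator or interval, but the documents do not show that. The arm proportions would in any case give an unadjusted difference.

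**Nothing is wrong with the test.** Adjusting only for the stratification factors is a standard, defensible choice. This stands in full.

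**The phase 3 consequence is easily overstated.** A reader might set the phase 3 size at the point estimate against the size at the lower confidence limit and blame the missing covariate. With placebo at 20%, 90% power and a pooled two-proportion formula, a difference of 0.20 needs 109 per arm, while the MH lower limit (0.20 - 0.143) needs about 1,140. That gap comes from having 74 per group. With adjustment the lower-limit figure is about 1,219 at r = 0, 1,101 at r = 0.3 and 876 at r = 0.5. It stays very large throughout and is worse if CDAI is not prognostic. Nor do the documents say that phase 3 would be sized at a lower limit. The contrast does not support this point.

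**The gain is assumption-driven.** Rates, SD, r and stratum prevalences are all assumed, and the entry range restricts the covariate. A correlation of 0.5 before restriction to 220-450 would be about 0.44 among enrolled subjects, with a variance ratio nearer 0.89 than 0.86. The main simulation also lets the strata carry no prognostic information. A run with small stratum effects gave much the same ratios at 20% v 40% (1.00 / 0.96 / 0.86), so this last reservation matters little; the others stand.

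**The MH interval alone would fix an estimator, and it agrees better with CMH.** True, and it should be reported. It does not use baseline CDAI, so the adjusted estimate still has a place as a supportive figure.

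**Conclusion.** The point holds as a minor improvement. In the available text, clinical remission has a valid stratified CMH test, and baseline CDAI is not used for the effect size wanted for phase 3.

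At an assumed 20% v 40% with 74 per group, adjustment changes the variance by about +1%, -4% and -14% at r = 0, 0.3 and 0.5 (repeat runs at r = 0.5: -11% to -16%). Across the rates for which half-widths were computed, the 95% interval goes from about 0.2 points wider to about 1 point narrower on each side. At r = 0.3 the gain is 0.1 points or less. If baseline CDAI does not predict remission, there is a small loss.

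The case for acting is that the cost is low and the estimator would be fixed in advance, which is useful whatever r proves to be. It does not rest on a large precision gain.

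**What to change.** Before the induction SAP is finalized, confirm whether it already names an estimator for clinical remission. If it does not, add:

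1. The stratified CMH test is the only source of the p-value and governs significance, including the step to the secondary endpoints.
2. The Mantel-Haenszel stratum-weighted difference in remission proportions (BT-11 minus placebo) is reported beside it with a 95% CI.
3. The supportive estimate for phase 3 planning is a standardised risk difference with a 95% CI from a logistic model with treatment, prior biologic use, baseline corticosteroid use and baseline CDAI, using a small-sample-corrected robust SE.

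If an estimator is already named, the sponsor need only check whether it uses baseline CDAI.

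The cost is a few sentences and a little programming, with no new data. There are two downsides. The interval is 0.1 to 0.2 points wider if baseline CDAI is not prognostic. The adjusted interval also disagrees with CMH on significance in about 2% to 12% of trials with a true effect, most often where the precision gain is largest. Naming CMH as governing in advance settles such disagreements, and the slight excess rejection at a low-rate null is a further reason not to take a p-value from the adjusted model.

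### Is the gate to the secondary endpoints unusable because it names one primary outcome while the plan has coprimary endpoints?

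*Combined protocol and SAP*

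**What the plan says.** The Statistical Methods section states "The first coprimary efficacy endpoint is the proportion of subjects achieving clinical remission at Week 12". It does not name the second coprimary. The Primary Objective in the synopsis speaks of "inducing clinical remission and endoscopic response at Week 12", so endoscopic response is the natural inference.

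The gate is worded in the singular: "If the primary outcome shows significance, tests will be conducted on secondary outcomes until a non-significant p-value is found". After the first non-significant result, the remaining tests become exploratory. The hierarchy is introduced for the secondary measurements only, and on their ranking the section says "The order of secondary endpoints is described above". No such list appears in the text available for review.

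The number of primary endpoints varies with the sentence. Study Design refers to an analysis "of the Week 12 primary endpoint, Week 12 key ranked secondary endpoints", and Statistical Methods to "A data lock and final induction phase analysis of the Week 12 primary endpoint", both singular. The closing paragraph of Statistical Methods uses the plural and declines any type I error adjustment because this analysis is the final one. The level is set once for everything: "Statistical tests will be 2-sided and performed at the 0.05 level of significance".

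Two statements limit what rests on significance. Study Design gives the purpose as "to estimate the effect size and efficiently power future phase 3 studies", and Statistical Methods says that the trial's success is not closely tied to significance on the primary and key secondary endpoints.

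**The concern.** A gate should give one answer for every pattern of results. With two coprimaries and a condition on a single outcome, an analyst facing one significant and one non-significant coprimary could ask whether the secondary tests are formal or exploratory. If that is settled only after the data are seen, the answer can be picked to suit the result.

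There is also an apparent error-rate problem. Every test is at two-sided 0.05, the hierarchy is described only for secondary measurements, and the reason given for no adjustment (a final analysis) deals with repeated looks rather than with several primaries. If either coprimary could be claimed alone, the chance of a false primary claim would exceed 5%.

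**Working it through.** **The readings against each result.** Two readings have support in the text: both coprimaries required (the usual meaning of coprimary, and consistent with the joint wording of the objective), or the first coprimary, remission, as the single primary outcome. A third, that either suffices, fits the singular wording least.

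| Remission | Endoscopic response | Gate if both required | Gate if remission alone |
|---|---|---|---|
| significant | significant | open | open |
| not significant | significant | closed | closed |
| not significant | not significant | closed | closed |
| significant | not significant | closed | open |

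Each reading can be applied to every row. They disagree only in the last.

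**Inputs.** Two-sided 0.05 comes from Statistical Methods (critical value 1.960). The section's only related figure is the evaluable number: 75 × (1 − 0.01) = 74.25, which agrees with the stated 74 or so per group. No power, event rate or correlation is given, so those below are assumptions. The two test statistics are taken as bivariate normal. At 80% power each has mean 1.960 + 0.842 = 2.802.

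**How often the readings disagree.** P(remission only) = P(remission significant) − P(both significant).

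| Test correlation | P(both), 80% power each | P(remission only) |
|---|---|---|
| 0 | 0.640 | 0.80 − 0.640 = 0.160 |
| 0.5 | 0.687 | 0.80 − 0.687 = 0.113 |
| 0.7 | 0.713 | 0.80 − 0.713 = 0.087 |
| 0.9 | 0.750 | 0.80 − 0.750 = 0.050 |

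The chance of any split result is twice this (0.32, 0.23, 0.17, 0.10), but the half in which only endoscopic response succeeds closes the gate under both readings. At 50% power each, the disputed case has probability 25%, 17%, 13% and 7%.

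Equal power matters to these figures. With 80% power for remission and 50% for endoscopic response, the disputed probability is 0.80 − 0.40 = 0.40 at correlation 0 and 0.80 − 0.456 = 0.344 at 0.5. With the powers reversed it is 0.50 − 0.40 = 0.10 and 0.50 − 0.456 = 0.044.

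**Type I error, both required.** With both coprimaries null, a false primary claim has probability 0.0025, 0.0093, 0.0165 and 0.0296 at correlation 0, 0.5, 0.7 and 0.9. If only one is null, it is at most 0.05.

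**Type I error, remission alone opens the gate and endoscopic response is not claimed separately.** This is a fixed sequence starting with remission. If remission is null, any false claim needs a false positive on remission, so error is at most 0.05. If remission works, error is limited by the first true null reached, again at most 0.05.

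**Each coprimary claimable alone at 0.05.** With both null, P(at least one) = 0.05 + 0.05 − P(both):

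- correlation 0: 0.10 − 0.0025 = 0.0975
- correlation 0.5: 0.10 − 0.0093 = 0.0907
- correlation 0.7: 0.10 − 0.0165 = 0.0835
- correlation 0.9: 0.10 − 0.0296 = 0.0704

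This excess needs a stand-alone claim on endoscopic response. The singular gate wording does not create it, and a rule that only delayed the secondary tests would not remove it.

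**The case for a change.** The best case for a change is that the sponsor chose to write a gate, so it should be explicit, and one sentence before unblinding would make it so. The disputed case need not be rare: if endoscopic response is the harder endpoint to move, the 40% above is nearer the mark than 16%. Under the remission-alone reading, the standing of endoscopic response is also awkward. It is tested at 0.05 as a coprimary, and nothing expressly bars a separate claim, which brings back the 7.0% to 9.75%.

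Much of this stands. The singular and plural wording is inconsistent, the text available does not state the rule, and the frequency of the disputed case depends on unknown powers. What does not stand is the step to a defect. The excess error rests on a claim that the plan does not make, and the usual meaning of coprimary excludes it. The section that should list the endpoints and their order is not in the text available, so silence here does not show that the plan lacks a rule. A proposed replacement would also do more than tidy the wording. Requiring both coprimaries, or ranking remission ahead of endoscopic response, is a choice of claim strategy with a price: at 80% power each, the secondary chain opens 64% to 75% of the time under either of those rules, against 80% if remission alone opens it. That trade-off belongs to the sponsor.

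**Conclusion.** No change to the plan follows. The mismatch is a slip in wording and a gap that an analyst would fill in the ordinary way, by reading coprimary as both required; error is then at most 5% and the absence of an alpha adjustment is correct. The other supported reading also gives a definite answer for every result and keeps error at or below 5%, provided endoscopic response is not claimed on its own.

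The two readings part only when remission alone is significant: 16% to 5% of the time over correlations 0 to 0.9 at an assumed 80% power each, and up to 40% in the unequal-power case shown. Even then, effect estimates, confidence intervals and the trial's validity are untouched. Only the formal or exploratory label on the secondary tests changes, and the plan itself places little weight on that label. Statistical Methods already requires the induction-period SAP to be approved before lock and unblinding, so the intended reading can be recorded there in the normal course.

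The conclusion assumes that endoscopic response is the second coprimary, which is inferred from the objective, and that no stand-alone claim on it is intended.
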